- 18 Can be performed up to 2 days prior to this visit.
- 19 At the EOC4, patients will be evaluated to determine if they have clinical benefit, as defined by IWG objective response (PR or CR) or subjective response (in the absence of objective response) and are tolerating the infusions well and who would like to continue to receive infusions until PD or other criteria for withdrawal are met as noted in [Section 3.3.4.1](#). For each infusion past the 4th cycle, patients will continue to be assessed after each cycle for clinical benefit (objective or subjective response), and that they are tolerating the infusions well and would like to continue until PD or other criteria for withdrawal are met as noted in [Section 3.3.4.1](#).
- 20 Procedures/assessments not mandatory after implementation of CTP version 5.0, but assessments (e.g. hematology & biochemistry laboratory tests, bone marrow aspirates) should be performed at the investigator's discretion, based on standard medical care. Findings are documented in the eCRF only if qualifying for and (S)AE.
- 21 After implementation of CTP version 5.0, vital signs are mandatory only at the day of administration of BI 836858, results will be documented in the eCRF only if qualifying for an adverse event.
- 22 After implementation of Protocol version 5.0, Collection of Concomitant Therapy information only if the indication is treatment of an Adverse Event.

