## FLOW CHART 2 – MAINTENANCE

Trial Periods	Maintenance Study Treatment**		FU
	Maintenance Cycles X (1 Cycle = 28 days)	EOT	FU (No further FU visits after EoR period upon implementation approval of CTP version 5.0)
Visit	MCX  V1		
Days (in respective cycle)*	1		
LABS/SAFETY ASSESSMENTS			
Safety laboratory parameters incl. urinalysis 	X 	X 	
Physical examination ECOG performance status	X 	X 	
Vital signs, weight	X 	X 	
Serum pregnancy test 	X	X	
12 lead-ECG		X 	
Adverse events	X	X	X 
Concomitant therapy	X 	X 	X 
DISEASE ASSESSMENTS			
Number of transfusions received	← X  →		
Bone marrow aspiration 	X 		
Cytogenetics and molecular genetics of MDS 			
Clinical Disease Assessment 	X 		

TRIAL MEDICATION			
Drug Administration (BI 836858)	X		
Best Supportive Care (Phase II Arm B only)	← X →		
Eligibility for subsequent cycles of study treatment 	X		
End of trial treatment	X 		
Other therapies for MDS (Phase II Only)			
Vital Status	X 		

**EOT:** End of Treatment. The EOT visit is to occur 28 days (+7 days) after the last administration of BI 836858. Patients who permanently discontinue study treatment will enter into Follow-up phase after EOT visit. Refer to [Section 3.3.4](#) for treatment discontinuation criteria. After implementation of CTP version 5.0, no further follow-up visits, unless follow-up is for S(AE) that occurred before EoR period.

**FU:** Follow-up starts 4 weeks after the EOT visit; Phase I patients: visits or telephone calls will occur at least every 4 weeks for 6 months. After the 6th follow-up visit, the patient will be considered off trial. Phase II patients: visits or telephone calls will occur at least every 4 weeks until 12 months after the last administration of BI 836858, after which these visits will occur every 6 months until the end of the trial. After implementation of CTP version 5.0, no further follow-up visits, unless follow-up is for S(AE) that occurred before EoR period.

\* The planned duration of a treatment cycle is 28 days; there will be one administration of BI 836858 per maintenance cycle, on Day 1.

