## 5.2 SAFETY

Recruitment in this trial was discontinued prematurely during the Phase I expansion cohort. With the aim to minimize the burden for trial participants, after approval of CTP version 5.0, the mandatory protocol procedures described below in [sections 5.2.2](#) Assessment of adverse events, [5.2.3](#) Assessment of safety laboratory parameters [5.2.4](#), Electrocardiogram, [5.2.5](#) Assessment of other safety parameters, and [5.3.1](#) Physical Examinations are reduced for all patients who continue to receive trial medication in treatment cycles  $\geq 5$ . Instead, safety assessments should be performed at the investigator's discretion, based on standard medical care. For details refer to Flow Chart.

Findings are documented in the eCRF only if qualifying for an adverse event (see [section 5.2.2](#), which remains unchanged).

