### 5.2.5 Assessment of other safety parameters

#### 5.2.5.1 Vital signs

Vital signs (blood pressure, heart rate and body temperature) will be recorded at every visit during screening, treatment, EOC4 and EOT. Additional time points for blood pressure and heart rate at the day of administration of BI 836858 are: prior to the start of premedication, prior to the start of BI 836858 infusion, and in 30 ( $\pm 10$ ) minute intervals throughout the course of the infusion of BI 836858 and 60 ( $\pm 10$ ) minutes after the end of the infusion, thereafter every 4-8 hours until at least 24 hours after start of the infusion. In case of an infusion-related reaction, the Investigator should decide whether to intensify or prolong monitoring of vital signs of the patient.

Beginning with infusion 2, blood pressure and heart rate will be assessed at the same time points as during infusion 1 with the exception that they will not be assessed every 4-8 hours until at least 24 hours after the start of the infusion.

After implementation of CTP version 5.0 the vital signs are mandatory only at the day of administration of BI 836858 (see above). Results will be documented in the eCRF only if qualifying for an adverse event.

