7.8.2 Laboratory data

The analyses of laboratory data will be descriptive in nature and will be based on BI standards (8). The same on-treatment period as considered for the analysis of AEs will be applied for laboratory values. Patients having at least one post-baseline laboratory value will be displayed in the descriptive analyses.

Safety laboratory examinations include hematology, biochemistry, coagulation and qualitative urine analysis:

| | |
|--------------|--|
| Hematology | Hemoglobin, red blood cell count (RBC), white blood cell count (WBC) with differential (neutrophils, basophils lymphocytes, monocytes, eosinophil, reticulocytes), platelets (PLT) |
| Biochemistry | Glucose (plasma), sodium, potassium, calcium, inorganic phosphate, creatinine, AST, ALT, alkaline phosphatase (AP), lactate dehydrogenase (LDH), bilirubin (total and direct), urea (preferred) or BUN, total protein, albumin, uric acid, IgG, IgM, IgA and direct antiglobulin (direct Coombs), Free haemoglobin(serum), Haptoglobin |
| Coagulation | Activated partial thromboplastin time (aPTT), prothrombin time (PT), international normalised ratio (INR) where indicated (e.g. treatment with vitamin K antagonists) |
| Urine | pH, glucose, erythrocytes, leukocytes, protein, nitrite |

Neutrophil and platelet counts of each patients will be plotted in log scale graphs.

Descriptive statistics, including change from baseline and frequency of patients with transitions relative to the reference range, will be provided. CTCAE grades for applicable laboratory parameters will be calculated according to CTCAE version 4.0. The following outputs will be presented:

- Worst CTCAE grade experienced during the on-treatment phase.
- Transitions of CTCAE grade from baseline to worst laboratory value, from worst to last laboratory value during the on-treatment phase, and from baseline to last laboratory value.

Worse laboratory value and its CTCAE grade (highest CTCAE grade) over all courses will be calculated for each laboratory parameter.

The last laboratory value on treatment is the laboratory value of the last visit during the on treatment period of each patient.

Patients with missing CTCAE grade at baseline or no baseline value but with post-baseline values will be displayed in the category “Missing CTCAE grade at baseline” for those laboratory parameters where CTCAE grading is applicable.

Possible clinically significant abnormal laboratory values:

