7.8.3 Vital signs

Only descriptive statistics are planned for the analysis of vital signs. Observed values and changes from baseline will be summarized.

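### SAP 7.8.2 and 7.8.3 carry last-value and change-from-baseline summaries past protocol version 5.0, after which late laboratory and vital-sign results are recorded only if they qualify as an adverse event

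*SAP*

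**What the plan says.** Protocol version 5.0 (revision of 11 September 2019) cuts back data collection. Protocol 5.2 says the mandatory procedures are "reduced for all patients who continue to receive trial medication in treatment cycles" 5 and later. Footnote 20 of Flow Chart 1 and footnote 12 of Flow Chart 2 are attached to the safety-laboratory row for those cycles and for the end-of-treatment visit. They leave the assessments to the investigator's discretion and add: "Findings are documented in the eCRF only if qualifying for and (S)AE". Vital signs must still be taken on dosing days, but Protocol 5.2.5.1 says: "Results will be documented in the eCRF only if qualifying for an adverse event". Footnotes 21 and 13 of the two charts say the same.

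The final SAP is dated 7 January 2020. SAP 6.1 sets the on-treatment period from first administration to 30 days after the last, and SAP 7.8.2 applies that period to laboratory values. SAP 7.8.2 defines the end point of its tables thus: "The last laboratory value on treatment is the laboratory value of the last visit during the on treatment period of each patient". It asks for change from baseline and for CTCAE transitions from baseline to worst, worst to last and baseline to last. For vital signs, SAP 7.8.3 says: "Observed values and changes from baseline will be summarized". SAP 6.6 leaves missing values missing. SAP 4.2 lists one change, the loss of Phase II, and does not mention the version 5.0 recording rule.

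**The concern.** A last-value or change table is readable only if the value was recorded for reasons unrelated to what it showed. From Cycle 5 under version 5.0 that no longer holds: a normal result is left out by rule, and a result that qualifies as an adverse event is kept in some form. The tables combine this period with the routine period before it and carry no flag.

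The patients concerned are not a random subset. Protocol 11.4 says those kept on treatment after recruitment stopped were those with clinical benefit, so they are likely to contribute the longest exposure. A reader would take a worst-to-last table as evidence of recovery or non-recovery at the end of treatment. For these patients it may show neither.

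**Working it through.** The plan gives no figure to reproduce, so the check is mainly of text, followed by an illustration.

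**1. Order of the documents.** The recording rule dates from 11 September 2019 and the SAP from 7 January 2020. SAP section 3 says the SAP assumes familiarity with the protocol and its amendments. The SAP could therefore have addressed the rule, and does not.

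**2. Scope.** Protocol 5.2 and 6.2 limit the reduction to cycles 5 and later. In Flow Chart 1 the laboratory and vital-sign entries for cycles 1 to 4 and for the end-of-Cycle-4 visit carry no version 5.0 footnote. The MTD evaluation period (SAP 5.1) lies within this untouched part.

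**3. Where a qualifying value is entered.** The documents do not say which eCRF page receives it. There are two cases:
- On the laboratory or vital-sign page: the late values in the tables are those that qualified as adverse events.
- On the AE page only: no late value reaches the tables, and the last on-treatment value is the last one before version 5.0, although it is labelled as end of treatment.

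**4. Which tables are exposed.** Worst-grade and baseline-to-worst tables depend on extremes, which the rule tends to keep. Last-value, worst-to-last, baseline-to-last and change-from-baseline tables depend on the ordinary late values, which it removes.

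**5. Illustration for the first case.** Document input: 21 + 6 = 27 Phase I patients (Protocol synopsis). Assumptions, none given in the documents: m visits after version 5.0; each independently yields a qualifying value with probability p; k patients are affected. The chance that a patient's last recorded value is a late qualifying one is 1 − (1 − p)^m. With complete recording, the chance that the last value is a qualifying one is p.

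| p | m = 1 | m = 3 | m = 6 | complete recording |
|---|---|---|---|---|
| 0.05 | 0.05 | 1 − 0.95³ = 0.143 | 1 − 0.95⁶ = 0.265 | 0.05 |
| 0.10 | 0.10 | 1 − 0.90³ = 0.271 | 1 − 0.90⁶ = 0.469 | 0.10 |
| 0.20 | 0.20 | 1 − 0.80³ = 0.488 | 1 − 0.80⁶ = 0.738 | 0.20 |

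The formula counts late values only. A patient with none falls back on the last routine value, which is not counted as abnormal here.

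The excess over all 27 patients is k × [1 − (1 − p)^m − p] / 27:
- p = 0.10, m = 6, k = 2: expected counts 0.94 against 0.20, an excess of 2.7 percentage points.
- Same p and m, k = 5: 2.34 against 0.50, 6.8 points.
- Same p and m, k = 10: 4.69 against 1.00, 13.7 points.
- Low end (k = 2, p = 0.05, m = 3): 0.29 against 0.10, 0.7 points.
- High end (k = 10, p = 0.20, m = 6): 7.38 against 2.00, 19.9 points.

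**The case against.** **Little rests on these tables.** They are descriptive, Phase II was dropped and development was discontinued. That stands and limits the importance of the point.

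**The second case in step 3 may be the true one.** Protocol 5.2.2.1 has clinically relevant laboratory and vital-sign changes recorded as adverse events, which can be read as the AE page alone. SAP 7.8.2 also relies on a sponsor laboratory standard that is not among the documents. A reader might infer that late values are certainly selected for abnormality; the documents do not support that certainty. The alternative is still a table labelled as end of treatment that stops earlier without saying so.

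**Few visits may be affected.** From 11 September 2019 to 7 January 2020 is 118 days, or 118/28 = 4.2 cycles, and the amendment needed approval first. The database-lock date is not given. Protocol 6.2.3.3 sends patients still on treatment while the final report is prepared to a revised report. So a striking figure should not be read into the illustration. A 15% rate over six visits gives 1 − 0.85⁶ = 0.62, but both inputs are assumed, and the result applies only to an unknown subset of the 27.

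**Transfusions.** The row "Number of transfusions received" carries the same footnotes, so a reader might infer that unrecorded transfusions would pass as transfusion independence. SAP 5.2.2 does not support this. It takes RBC transfusion independence and the haematologic improvement endpoints from the investigator's entry on the Disease Assessment eCRF and plans no derivation from the blood-product page. A blank transfusion page therefore cannot itself create a response, and a skipped disease assessment yields no reported response.

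**A blanket cut would do harm.** Ending every laboratory summary at version 5.0 would drop real late abnormalities from the worst-grade, clinically significant and hepatic outputs. This is right, and the fix is limited accordingly.

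**Conclusion.** The concern holds in limited form. The collection rule and the planned tables do not fit together for laboratory and vital-sign data from Cycle 5 onward under version 5.0. As written, the affected tables either mix routine values with value-selected ones or stop silently before the end of treatment; the documents do not settle which. The size is unknown and may be small. The 0.7 to 19.9 points above assume the first case, independence between visits, and invented values of p, m and k. In the second case there is no inflation of this kind, only mislabelling. The point does not reach the MTD and DLT results, data through the end-of-Cycle-4 visit, or the transfusion-independence and haematologic improvement endpoints. It is a cheap improvement to descriptive reporting.

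**What to change.** In SAP 7.8.2 and 7.8.3, restrict the last-value, worst-to-last, baseline-to-last and change-from-baseline summaries to data up to each patient's last visit before version 5.0 took effect at the site, or the end-of-Cycle-4 visit if that is later. List later values separately, marked as recorded because of an adverse event. State which eCRF page receives them, and note the change in SAP 4.2.

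Keep worst CTCAE grade, baseline-to-worst transitions, possible clinically significant abnormalities, and the hepatic injury and potential Hy's law analyses on the full on-treatment period, so that no late safety signal is lost. Make no change to RBC transfusion independence or haematologic improvement in SAP 5.2.2.

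The cost is a few sentences in the SAP and one implementation date per site. The downside is shorter follow-up for long-term patients in the last-value and change tables.

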### 3.3.3 Exclusion criteria

1. Patient with IPSS category of Int-2 or high-risk MDS.
2. Phase II only: Patients with a deletion 5q cytogenetic abnormality.
3. Treatment within 28 days prior to Cycle 1 Day 1 with: i) long acting erythropoiesis stimulating agents, ii) long acting Granulocyte colony-stimulating factor (G-CSF), iii) granulocyte- macrophage colony stimulating factor (GM-CSF), iv) 5-aza, lenalidomide or decitabine, or v) iron chelation and within 14 days prior to Cycle 1 Day 1 with short acting erythropoiesis stimulating agents and short acting G-CSF.
4. Patient previously received allogeneic bone marrow or stem cell transplantation.
5. Second malignancy currently requiring active therapy (except for hormonal/anti-hormonal treatment, e.g. in prostate or breast cancer).
6. Neutrophils <1000 / $\mu$ L ( $1.0 \times 10^9$ /L).

Proprietary confidential information.

7. Aspartate amino transferase (AST) or alanine amino transferase (ALT) > 2.5 times the upper limit of normal (ULN).
8. Bilirubin >1.5 mg/dL, except for Gilbert's Syndrome or hemolysis.
9. Serum creatinine >2.0 mg/dL.
10. Known human immunodeficiency virus (HIV) infection and/or active hepatitis B infection (defined as presence of Hep B DNA), active hepatitis C infection (defined as presence of Hep C RNA)
11. Presence of concomitant intercurrent illness, or any condition which in the opinion of the Investigator, would compromise safe participation in the study, e.g. active severe infection, unstable angina pectoris, new onset of exacerbation of a cardiac arrhythmia.
12. Psychiatric illness or social situation which in the opinion of the Investigator would limit compliance with trial requirements.
13. Patient receiving concomitant therapy, which in the opinion of the Investigator is considered relevant for the evaluation of the efficacy or safety of the trial drug (refer to [Section 4.2.2](#)).
14. Female patients of childbearing potential who are sexually active and unwilling to use a medically acceptable method of contraception during the trial and for 6 months after the last administration of BI 836858, i.e. combination of two forms of effective contraception (defined as hormonal contraception, intrauterine device, transdermal patch, implantable or injectable contraceptive, bilateral tubal ligation etc.).
  - Women of childbearing potential are defined as females who:
    - Have experienced menarche and

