#### Protocol-specified Adverse Events of Special Interest (AESI)

The following are considered as Protocol-specified Adverse Events of Special Interest:

- Infusion-related reactions (CTCAE grade 3 or higher)
- Any event that qualifies for a dose limiting toxicity (refer to [Section 5.2.1.1](#))
- Drug Induced Liver Injury (DILI)

Hepatic injury defined by the following alterations of liver parameters:

- For patients with normal liver function (ALT, AST and bilirubin within normal limits) at baseline an elevation of AST and/or ALT  $\geq 3$  fold ULN combined with an elevation of total bilirubin  $\geq 2$  fold ULN measured in the same blood draw sample.
  - Patients showing these lab abnormalities need to be followed up according to [Section 10.1.2](#) of this clinical trial protocol (CTP) and the "DILI checklist" provided in the ISF.
- For patients with impaired liver function at baseline an elevation of AST and/or ALT  $\geq 5$  fold ULN combined with an elevation of total bilirubin  $\geq 2$  fold ULN measured in the same blood draw sample.
  - Patients showing these lab abnormalities need to be followed up according to [Section 10.1.2](#) of this clinical trial protocol and the "DILI checklist" provided in ISF.

AESI are to be reported in an expedited manner similar to Serious Adverse Events (within 24 hours), even if they do not meet any of the seriousness criteria - for details please see [Section 5.2.2.2](#).

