#### 10.1.2 Procedures

Repeat the following lab tests: ALT, AST, and bilirubin (total and direct) - within 48 to 72 hours. If ALT and/or AST  $\geq 3$  fold ULN combined with an elevation of total bilirubin  $\geq 2$  fold ULN (for normal values at baseline/screening) are confirmed, results of the laboratory parameters described below must be made available to the investigator and to BI as soon as possible.

In addition,

- obtain a detailed history of current symptoms and concurrent diagnoses and medical history according to the “DILI checklist” provided in the ISF
  - obtain history of concomitant drug use (including non-prescription medications, herbal and dietary supplement preparations), alcohol use, recreational drug use, and special diets according to the “DILI checklist” provided in the ISF;
  - obtain a history of exposure to environmental chemical agents (consider home and work place exposure) according to the “DILI checklist” provided in the ISF;
- and report these via the CRF.

Provide abdominal ultrasound or other appropriate imaging to rule out biliary tract, pancreatic or intrahepatic pathology, e.g. bile duct stones or neoplasm.

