- adverse events of special interest (AESIs) including infusion related reactions (IRRs).

In addition, tables will be provided for patients with AEs of incidence $\geq 10\%$ and with drug-related AEs of incidence $\geq 10\%$.

Tabulations of AEs using user-defined AE categories will also be provided.

Adverse events of special interest (AESIs):

Adverse events of special interest (AESIs) are defined in CTP section 5.2.2.1 as infusion related reactions (IRRs) of CTCAE grade ≥ 3 , DLTs (occurring during the MTD evaluation period or repeated treatment courses) and drug induced liver injury (DILI).

Other significant AEs:

Other significant AEs are defined as serious and non-serious AEs that lead to dose reduction or permanent discontinuation of study medication. Their incidence will be reported by severity according to CTCAE grades.

Infusion related reactions (IRRs):

IRRs will be the object of special attention.

Patients with any IRR will be tabulated by treatment and worst CTCAE grade. In addition, the number of infusions and the number of IRRs will be displayed by treatment.

The duration of IRR [h] and the time since start of the respective infusion [min] together with IRR related symptoms will be tabulated by infusion number and overall.

- Duration of IRR [h] = (End time of IRR - Start time of IRR) [seconds] / 3600
- Time since start of the respective infusion [min] = (Start time of IRR - Start time of infusion) [seconds] / 60

The relationship between the occurrence of IRRs and infusion rate as well as the administration of premedication will be examined.

Duration of IRR, time since start of infusion, and related symptoms will be summarized descriptively by infusion timepoints.

Fatal AEs:

AEs leading to death during the on-treatment period will be tabulated. Reported fatal AEs that occurred in the post-treatment phase will be listed.

Additionally, a table summarizing the information on deaths collected on the AE eCRF and the Patient Status eCRF will be provided.

User defined AE categories (UDAEC):

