In CTCAE Version 4.0 a 24 hours urine sample should be performed if the dipstick measurement is at least "2+" and the CTCAE grade should then be determined based on the 24 hours urine sample. Urine protein 1.0 – 3.4 g/24hrs is graded as CTCAE grade 2 and urine protein ≥ 3.5 g/24hrs is graded as CTCAE grade 3. As this definition aggregates different urine analysis measurements, this will not be considered for laboratory analyses, but should be considered by the investigator when grading adverse events.

To ensure medically rational and consistent (within BI) handling of urine protein assessed by dipstick only, no analyses based on CTCAE grades will be done. Instead urine protein will be

converted as for other urine measurements based on dipsticks (outlined in [Table 7.8.2:1](#)) and displayed in the urine analysis tables.

Hepatic injury:

As defined in the CTP a hepatic injury (DILI) is defined by the following alterations of hepatic laboratory parameters:

- an elevation of AST and/or ALT >3 fold ULN combined with an elevation of total bilirubin >2 fold ULN measured in the same blood draw sample, and/or
- marked peak aminotransferase (ALT, and/or AST) elevations ≥ 10 fold ULN

Potential Hepatic enzyme elevations (potential Hy's law cases):

In addition, the following definition of potential Hy's law cases was discussed with the FDA at the pre-NDA meeting of the NSCLC submissions of the nintedanib trials 1199.13 and 1199.14 and was agreed by the authorities. Please also refer to the FDA guideline Guidance for Industry Drug- Induced Liver Injury: Premarketing Clinical Evaluation, version of July 2009.

These are defined as those cases where a combination of all of the following events occurred: any on-treatment value of ALT or AST (or both) > 3 times upper limit of normal (3 x ULN) with total bilirubin ≥ 2 x ULN and ALKP < 2 x ULN. The events can occur in any order, but must occur within 14 days of the previous event, i.e. the second event must occur within 14 days of the first event, and the third event must occur within 14 days of the second event, etc. [Figure 7.8.2:1](#) gives 2 examples, first where the criterion is satisfied and second where it is not satisfied.

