All of the above combinations of elevated liver enzymes will be analysed, i.e. DILI cases as defined in the CTP and additionally the definition of potential Hy's law cases which was discussed with the FDA by the nintedanib project. A listing with detail hepatic enzymes values will be created for the subjects who satisfied the condition. eDISH plot for ALT and total bilirubin will be displayed.

Potential Hy's Law cases

[figure not shown]

Figure 7.8.2:1 Assessment of patients fulfilling the criteria for potential Hy's law cases. Top: patient fulfils criteria. Bottom: patient does not fulfil criteria.

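### SAP 7.8.2 credits the protocol with a DILI definition that differs from protocol 5.2.2.1, so DILI labelled as CTP-defined can disagree with the AESI table

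*SAP*

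**What the plan says.** Protocol 5.2.2.1 lists DILI as one of three adverse events of special interest (AESIs) and defines it in two tiers. Both tiers require the enzyme and bilirubin elevations in the same blood sample. The first tier applies when ALT, AST and bilirubin are normal at baseline. The second begins "For patients with impaired liver function at baseline an elevation of AST and/or ALT" and sets a higher aminotransferase threshold. Protocol 10.1.2 again ties the lower threshold to patients with normal baseline values ("fold ULN (for normal values at baseline/screening) are confirmed").

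SAP 7.8.2 introduces its own rule with "As defined in the CTP a hepatic injury (DILI) is defined by the following alterations of hepatic laboratory parameters". That rule has two parts joined by and/or. One is "an elevation of AST and/or ALT >3 fold ULN combined with an elevation of total bilirubin >2 fold ULN" in the same sample, for every patient. The other is "marked peak aminotransferase (ALT, and/or AST) elevations" of at least 10×ULN, with no bilirubin condition. Later in the same section the SAP says the analysis will cover "DILI cases as defined in the CTP", together with potential Hy's law cases, which it presents openly as an addition.

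SAP 7.8.1.2 plans a separate AESI table and takes the AESI definitions, DILI included, from CTP section 5.2.2.1. SAP 4.1 and 4.2 record only a clarification of the DLT endpoint and the dropping of Phase II.

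**The concern.** The SAP uses one label for two rules. The AESI table rests on protocol 5.2.2.1; the laboratory analysis rests on a different rule credited to the same source. A programmer following the SAP literally would flag patients as CTP-defined DILI whom the protocol does not define that way.

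DILI carries 24-hour reporting under the protocol. With few patients, a single person shown as CTP-defined DILI in the laboratory output but absent from the AESI table would stand out. It could be read as a missed expedited report, or the wrong DILI count could be quoted.

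**Working it through.** Notation: AT is the higher of AST and ALT, and B is total bilirubin, both as multiples of ULN in the same sample. Impaired baseline is read as any of ALT, AST or bilirubin outside normal limits, the complement of the protocol's first tier.

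**The rules side by side**

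| | Protocol 5.2.2.1 | SAP 7.8.2 (DILI) |
|---|---|---|
| Normal baseline | AT ≥ 3 and B ≥ 2 | (AT > 3 and B > 2) or AT ≥ 10 |
| Impaired baseline | AT ≥ 5 and B ≥ 2 | same as above |
| AT alone | none (nor in 10.1.2) | AT ≥ 10 |

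There are three differences: the baseline split and 5× tier are gone, a stand-alone 10× criterion is added, and ≥ becomes > in the combined rule.

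**Where they disagree**

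SAP yes, protocol no:
- Impaired baseline, 3 < AT < 5 and B > 2. Example: AT = 4, B = 2.5. SAP: 4 > 3 and 2.5 > 2, so yes. Protocol: 4 < 5, so no.
- Either baseline, AT ≥ 10 and B < 2. Example: AT = 12, B = 1. SAP: 12 ≥ 10, so yes. Protocol: 1 < 2, so no.

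Protocol yes, SAP DILI rule no:
- Normal baseline, AT exactly 3 with B ≥ 2.
- B exactly 2, with AT from 3 (normal baseline) or 5 (impaired baseline) to below 10.

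The SAP's Hy's law rule (AT > 3, B ≥ 2, ALKP < 2×ULN) still flags the B = 2 cases with AT above 3 if ALKP is below 2×ULN. On a single sample, AT exactly 3 in a normal-baseline patient is the only case that both SAP rules miss whatever the ALKP.

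**Grid check** (AT 0.1 to 15.0, B 0.1 to 5.0, steps of 0.1; 150 × 50 = 7,500 points per baseline stratum)

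| Baseline | SAP only | Protocol only |
|---|---|---|
| Normal | 51 × 19 = 969 (AT ≥ 10, B < 2) | 31 (AT = 3.0) + 69 (B = 2.0, AT 3.1–9.9) = 100 |
| Impaired | 969 + 19 × 30 = 969 + 570 = 1,539 | 50 (B = 2.0, AT 5.0–9.9) |

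Every protocol-only point lies on a boundary. The Hy's law rule with ALKP < 2×ULN recovers the 69 and the 50 but not the 31. The counts depend on the range chosen and are not patient rates. A wider grid (AT to 20, B to 10) gives 1,919 and 3,439 SAP-only points against 150 and 50 protocol-only points: the same regions and the same direction.

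**Can impaired-baseline patients be enrolled?** Yes. Exclusion 7 removes only AST or ALT above 2.5×ULN, so values above 1× and up to 2.5×ULN are eligible. Exclusion 8 reads "Bilirubin >1.5 mg/dL, except for" Gilbert's syndrome or hemolysis. Exempt patients have no stated bilirubin cap and could meet the bilirubin part at baseline.

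**Is it a declared change?** No. SAP section 4 is silent, and the readable amendment log shows no change to the DILI definition. The SAP was finalised on 07-JAN-2020, after the protocol revision of 11 SEP 2019, so it should match the current text.

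**The case against.** The strongest reply is that little depends on this. The AESI table already points to protocol 5.2.2.1, so only a supplementary laboratory display is affected. The SAP gives the liver listing no title, so two identically labelled outputs are an inference. AESIs are reported by investigators while the display is derived from laboratory values, so the two could differ even under one rule. The listing shows detailed enzyme values and there is an eDISH plot, so with baseline values a reader could reclassify a 4×/2.5× or 12×/1× patient. No discordant patient is shown, and over-inclusion does not hide a liver signal.

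Much of this stands. It limits the consequence, and the > versus ≥ difference matters hardly at all. The Hy's law rule also links values up to 14 days apart, so a neighbouring sample may capture a boundary case. Aligning the rules removes one source of disagreement, not all of them.

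It does not touch the core point. The SAP says the rule is the protocol's, and it is not. The phrase "DILI cases as defined in the CTP" describes what will be analysed whatever the listing is called. A reader who has to rework the classification by hand has not been given the analysis the label promises.

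**Conclusion.** The concern holds and should be fixed. SAP 7.8.2 misattributes its DILI rule to the protocol, and the resulting disagreement is almost wholly over-inclusion: impaired baseline with AT between 3× and 5×ULN and bilirubin above 2×ULN, and any baseline with AT of at least 10×ULN and bilirubin below 2×ULN. Under-inclusion is confined to exact threshold values.

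The affected outputs are descriptive and cover 27 patients (21 in escalation plus 6 in expansion, from the protocol synopsis). The MTD, the DLT count and the primary endpoints do not change. The documents give no rate of liver-enzyme elevations, so no expected number of discordant patients is claimed.

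The conclusion assumes that both passages are reproduced intact, that impaired means not normal at baseline, and that baseline follows SAP 6.7. It does not say which threshold is clinically right.

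**What to change.** Reconcile protocol 5.2.2.1 with SAP 7.8.1.2 and 7.8.2 so that label and rule agree:

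- Any output described as DILI as defined in the CTP applies the 5.2.2.1 text, with the baseline tier taken from SAP 6.7.
- If the criterion of at least 10×ULN is kept, report it as a separately named laboratory category, as the SAP already does for potential Hy's law cases.
- If the SAP rule was intended, declare it in SAP 4.2 and stop attributing it to the protocol.

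Add one sentence on data completeness. After protocol version 5.0, safety laboratory tests from cycle 5 onward are at the investigator's discretion, and findings reach the eCRF only if they qualify as an adverse event. Adverse event reporting under 5.2.2 is unchanged, so a recognised DILI remains reportable, but a laboratory derivation may be incomplete for those cycles under either rule.

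The cost is a few lines of SAP text and one derivation flag from recorded laboratory data. The flag cannot recover values that were never entered.
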